6.5. Study Drug Compliance

For subjects in the safety evaluable population, overall compliance (%) for epacadostat will be calculated for all subjects as follows:

overall compliance (%) = $100 \times (\text{total dose taken}) / (\text{intended dose})$.

The intended dose will be determined up to the earliest study day of permanent discontinuation of epacadostat (ie, AE discontinuation is the first AE with action taken being "drug withdrawn"), last study drug record in the database, or subject death. Intended dose is defined as the sum of the doses prescribed by the investigator accounting both for planned dose reductions as well as those reductions or increases mandated by the investigator.

6.6. Medical History

For subjects in the safety evaluable population, medical history will be summarized by assigned treatment group. This summation will include the number and percentage of subjects with significant medical history for each body system/organ class and documented on the Medical History eCRF.

6.7. Prior and Concomitant Medication

For subjects in the safety evaluable population, prior medications and concomitant medications will be coded using the WHO Drug Dictionary and summarized by WHO drug class and WHO drug term. In the data listing, each medication will be recorded as prior, concomitant, or both prior and concomitant. Results will be summarized as number and percentage of subjects with prior and concomitant medications by WHO drug term and WHO drug class.

Prior medication information will also be used to identify anticancer medication received by subjects before enrollment into the study. Prior anticancer medication data will be summarized and presented by treatment group as well as listed.

7. EFFICACY

The list of table and listing displays are provided in Appendix E.

7.1. General Considerations

Not applicable.

7.2. Efficacy Hypotheses

Objective Response Rate (Primary Endpoint): Administration of epacadostat in combination with pembrolizumab increases ORR by irRECIST in Phase 2 subjects with various tumor types compared with historical rate.

7.3. Analysis of the Primary Efficacy Parameter

7.3.1. Primary Efficacy Analysis

The primary variable for the Phase 2 expansion portion of the study is ORR, which is defined as the proportion of subjects with best overall response (CR or PR) by irRECIST v1.1 for select solid tumors and modified Lugano Classification (Cheson et al 2014) for DLBCL. Subjects' overall response will be evaluated as CR, PR, SD, PD, or not evaluable (NE) at each postbaseline radiological assessment based on changes in target lesions, nontarget lesions, and appearance of new lesions. The best overall response will be determined from response assessments before and including the date of starting new anticancer therapy. If any alternative cancer therapy is taken while on study, any subsequent assessments will be excluded from the best overall response determination.

For subjects with measurable disease at baseline, the irRECIST version 1.1 assessment criteria presented in Table 5 can be used to determine the overall response at a given timepoint based on the target lesion, nontarget lesion, and new lesion assessment.

Target Lesions	Nontarget Lesions	New Lesions	Overall Response
CR	CR	No	CR
CR	Non-CR / Non-PD	No	PR
CR	NE	No	PR
PR	Non-PD or NE	No	PR
SD	Non-PD or NE	No	SD
Not all evaluated	Non-PD	No	NE
PD	Any	Yes or No	PD
Any	PD	Yes or No	PD
Any	Any	Yes	PD

Table 5: irRECIST for Overall Response: Measurable Disease at Baseline

A subject is considered an objective responder as assessed by irRECIST if they have an overall response of CR or PR at any postbaseline visit. The proportion of responders within each treatment group will be estimated with 90% confidence intervals (CIs) by treatment group. Confidence intervals will be calculated based on the Clopper-Pearson method for binomial distributions. Within each treatment group, 1 sample binomial test will be used to test the null hypothesis.

Using irRECIST criteria, a PD needs to be confirmed as follows.

For each PD, if there is a second PD on the first response assessment that was \geq 4 weeks after the PD, then the PD is defined as confirmed, and the date of progression is the date of the first PD. Otherwise the PD is defined as unconfirmed.

If a subject had an unconfirmed PD, and there are no valid response assessments after that PD (not NE or missing), then the PD will be counted as follows:

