### 6.2.1. Second Course Period (Re-Treatment Period)

Subjects who stop MK-3475 with SD or better may be eligible for up to 1 year of additional combination therapy if they experience disease progression after stopping the combination study treatment. This re-treatment is termed the second course period of this study and is only available if the study remains open and the subject meets either one of the following conditions.

- 1a. Stopped initial treatment of the combination after attaining an investigator-determined confirmed CR according to RECIST v1.1.
  - Was treated for at least 24 weeks before discontinuing therapy.
  - Received at least 2 cycles of the combination (2 doses of MK-3475 and at least 80% of the planned doses of INCB024360) beyond the date when the initial CR was declared.

**OR**

- 1b. Subject had SD, PR, or CR and stopped after 24 months (35 administrations of MK-3475) of study therapy for reasons other than disease progression or intolerability.

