**Table 16: Imaging and Treatment After First Radiographic Evidence of Progressive Disease**

	Clinically Stable		Clinically Unstable	
	Imaging	Treatment	Imaging	Treatment
First radiologic evidence of PD	Repeat imaging at $\geq 4$ weeks to confirm PD	May continue study treatment at the investigator's discretion while awaiting confirmatory scan	Repeat imaging at $\geq 4$ weeks to confirm PD if possible	Discontinue treatment
Repeat scan confirms PD	No additional imaging required	Discontinue treatment	No additional imaging required	N/A
Repeat scan shows SD, PR, or CR	Continue regularly scheduled imaging assessments every 12 weeks	Continue study treatment at the investigator's discretion	Continue regularly scheduled imaging assessments every 12 weeks	May restart study treatment if condition has improved and/or clinically stable per investigator's discretion

In determining whether the tumor burden has increased or decreased, investigators should consider all target lesions as well as nontarget lesions. Subjects who are deemed clinically unstable are not required to have repeat imaging for confirmation. If radiologic progression is confirmed, then the subject will be discontinued from study treatment as specified in the Protocol, and the first radiographic evidence of PD should be the date of progression. If radiologic progression is not confirmed, then the subject should resume/continue study treatment and have their next scan according to the Protocol-specified schedule. If progression is not confirmed and the subject continues on treatment, the next scan that documents disease progression (and is confirmed by a second scan at least 4 weeks later), will be considered the date of disease progression.

NOTE: If a subject with confirmed radiographic progression (ie, 2 scans at least 28 days apart demonstrating progressive disease) is clinically stable or clinically improved, and there is no further increase in the tumor dimensions at the confirmatory scan, an exception may be considered to continue treatment upon consultation with the sponsor. Clinically stable subjects should also have at the confirmatory scan no further increase in the target lesions, no unequivocal increase in nontarget lesions, and no additional new lesions develop (nonworsening PD) to continue study treatment.

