### 9.4. Statistical Analyses

#### 9.4.1. Primary Analyses

Primary efficacy analysis will be conducted for the Phase 2 efficacy evaluable population. The primary variable for the Phase 2 expansion portion of the study is ORR, which is defined as the proportion of subjects with best response (CR or PR) by irRECIST v1.1 for select solid tumors and modified Lugano Classification (Cheson et al 2014) for DLBCL. The 95% exact CI for the ORR will be estimated using the Clopper-Pearson method. One sample binomial test will be used to test the null hypotheses.

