7.4.3. Progression-Free Survival

Progression-free survival is defined as the number of days from the date of first dose (which is not necessarily Day 1) to the earlier of death or disease progression by irRECIST v1.1 for selected solid tumors and the modified Lugano Classification for DLBCL. Date of death will be determined using the Death Report, the Survival Follow-Up, and the Subject Status eCRFs. Disease progression is defined as progression confirmed by a second, consecutive assessment at least 4 weeks apart with the option for continuing treatment while awaiting radiologic confirmation of progression. Censoring for PFS will follow the algorithm outlined in Table 6, which is based on FDA guidance (FDA 2007). Note that the Protocol mandates radiological evaluation of subjects every 9 weeks for the first 18 months and then may be done every 12 weeks thereafter. The analyses will be based on the efficacy evaluable population, according to treatment assignment. Time-to-event data will be analyzed by the Kaplan-Meier method.

Situation	Outcome	Date of Progression or Censoring
No baseline tumor assessments	Censored	Treatment start date
Progression documented between scheduled visits	Progressed	 Earliest of: Date of radiological assessment showing new lesion (if progression is based on new lesion); or Date of last radiological assessment of measured lesions (if progression is based on increase in sum of measured lesions)
No progression	Censored	Date of last valid radiologic assessment (not NE and not missing)
Treatment discontinuation for undocumented progression	Censored	Date of last valid radiologic assessment (not NE and not missing)
Treatment discontinuation for toxicity or other reason	Censored	Date of last valid radiologic assessment (not NE and not missing)
New anticancer treatment started	Censored	Date of last valid radiologic assessment (not NE and not missing)
Death before first PD assessment	Progressed	Date of death
Death between adequate assessment visits	Progressed	Date of death
Death or progression after more than 1 missed assessment	Censored	Date of last valid radiologic assessment (not NE and not missing)

Table 6: Evaluation and Censoring of Progression-Free Survival

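### The best-overall-response window does not close at confirmed progression, so a CR or PR first seen after it counts in the primary ORR for a subject who already has a PFS event

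*SAP*

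**What the plan says.** SAP 7.3.1 defines ORR as the proportion with a best overall response of CR or PR. It gives one time limit, "The best overall response will be determined from response assessments before and including the date of starting new anticancer therapy", and adds that once an alternative cancer therapy is taken, "any subsequent assessments will be excluded from the best overall response determination". A subject is an objective responder "if they have an overall response of CR or PR at any postbaseline visit". Protocol 9.4.1 defines ORR as the "proportion of subjects with best response (CR or PR) by irRECIST v1.1" and gives no window.

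The same SAP section sets out when a PD is confirmed. It dates progression at the first PD of the confirmed pair and counts a confirmed PD as an event. It does not say that later scans leave the response determination. PFS (SAP 7.4.3) runs "to the earlier of death or disease progression by irRECIST v1.1".

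Two Protocol provisions allow scans after confirmed PD:

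- **Continuation.** Section 5.8 and the note under Table 16 in 7.6.3.1 provide that, for a clinically stable or improved subject with confirmed progression, "an exception may be considered to continue treatment upon consultation with the sponsor".
- **Second course.** Under 6.2.1, subjects whose disease was at least stable when they stopped "may be eligible for up to 1 year of additional combination therapy if they experience disease progression after stopping the combination study treatment". Entry requires confirmed PD, and Section 6 applies the full assessment schedule to re-treatment.

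**The concern.** Neither route involves a new anticancer therapy in the ordinary sense, because the subject is on study drug. Protocol 6.4.2 also names re-treatment separately from new antineoplastic therapy. So the only stated cutoff does not clearly remove these scans, and a programmer following SAP 7.3.1 as written would count a CR or PR found on them.

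ORR is tested in single-arm cohorts against a fixed historical rate, and an open window can only add responders. The endpoints also stop agreeing within a subject. PFS ends at the confirmed PD. Duration of response (SAP 7.4.2) starts at the later CR or PR and looks only for PD after it. Duration of disease control (SAP 7.4.4) ends at the first PD, before the response that gives the subject a best response of CR or PR.

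**Working it through.** **1. The rule applied to one subject.** Take PD at Week 9, PD again at Week 13, treatment continued by exception, and PR at Week 30 with no new anticancer therapy.

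| Endpoint | Rule | Result |
|---|---|---|
| PFS | SAP 7.3.1 and 7.4.3: dated at the first PD of the confirmed pair | Event at Week 9 |
| ORR | SAP 7.3.1: CR or PR at any visit before new therapy | Responder at Week 30 |
| Duration of response | SAP 7.4.2: from first response to death or later PD | Starts at Week 30, 21 weeks after the PFS event |

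**2. Who can reach this by re-treatment.** Protocol 6.2.1 condition 1a requires a CR, so that subject already counts. Condition 1b admits SD, PR or CR after 24 months (35 administrations), so only an SD subject can become a new responder. Amendment 10 (02 JUL 2018) removed the option for anyone who had not started. From the amendment dates in Protocol Appendix K:

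- Gastric and HCC (Amendment 7, 15 FEB 2017): 502 days, about 16.5 months, before Amendment 10.
- Refractory and relapsed melanoma (Amendment 8, 30 AUG 2017): 306 days, about 10 months.
- MSI-high CRC (Amendment 6, 12 JUL 2016): 720 days. Thirty-five infusions 21 days apart take 34 × 21 = 714 days, which leaves 6 days for progression and a confirmation scan at least 4 weeks later.

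The first four cohorts could not use this route, and MSI-high CRC practically could not. RCC (Amendment 5, 11 JAN 2016) could do so only from about the turn of 2017 to 2018.

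**3. Reproducing the plan's figures.** SAP Table 4, ovarian: H0 20%, Ha 40%, one-sided 5%, power 80%, 10% loss.
n = [(1.645·√(0.20·0.80) + 0.842·√(0.40·0.60)) / 0.20]² = 28.6, rounded up to 29; 29/0.9 = 32.2, rounded up to 33, as stated. The other 11 single-stage sizes also reproduce, and the total is 446. The point does not dispute the design.

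**4. What one subject does.** Exact one-sided binomial p = P(X ≥ r | N, H0):

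| Cohort | Count | p | One more responder | p |
|---|---|---|---|---|
| Ovarian (H0 20%) | 11/33 | 0.051 | 12/33 | 0.022 |
| Checkpoint-naïve melanoma (H0 32%) | 18/40 | 0.058 | 19/40 | 0.029 |

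One responder moves ORR by 1/42 = 2.4 to 1/25 = 4.0 percentage points across the single-stage cohorts.

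**5. Illustration only.** The documents give no rate of response after confirmed PD. Assume a share f of all non-responders gains one, so that under H0 the rate becomes p0 + (1 − p0)·f. Keep the critical count fixed and take full planned N:

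| Cohort (critical count) | f = 0 | 0.25% | 0.5% | 1% |
|---|---|---|---|---|
| RCC (14/36) | 4.6% | 4.9% | 5.2% | 5.8% |
| Ovarian (12/33) | 2.2% | 2.3% | 2.5% | 2.9% |

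At f = 1%, the eight single-stage cohorts that Protocol Table 3 does not mark as discontinued early range from 2.9% to 5.8%. Only RCC passes 5%.

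**The case against.** The strongest reply is that this will rarely happen. Once PD is confirmed, Table 16 calls for stopping treatment and requires no further imaging, and Protocol 7.6.2 runs imaging only to documented progression. The exception needs sponsor consultation and no further tumor growth at the confirmatory scan. A later PR must be measured against the pre-treatment baseline, which SAP 4.1.4 does not reset, and SAP Table 5 scores any new lesion as PD. All of this stands as a limit on frequency. These are conduct and measurement rules, though, and none removes a qualifying scan from the response determination.

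Two further replies stand in part. New anticancer therapy is undefined, so the sponsor may mean it to include re-treatment; if so the SAP should say so, and the continuation route would remain open. The SAP also relies on published response criteria that are not reproduced in full, and those may end best response at progression. That cannot be checked here, and the any-visit wording in SAP 7.3.1 points the other way.

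A reader might infer that counting any response after a PD is wrong. The documents do not support that. Protocol 1.5.1 and 7.6.3.1 deliberately allow for response after an initial PD that repeat imaging does not confirm. The gap concerns confirmed PD only.

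**Conclusion.** The rule as written is wrong at one point: it lets a subject be a primary-endpoint responder after that subject's PFS event. The main route is treatment continued by exception. Re-treatment is a small residual route, limited to first-course SD subjects who restarted before Amendment 10.

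The number affected is probably small and cannot be computed from the documents. The direction is certain, and the one-subject examples need no assumed rate, only that the cohort reached its planned size.

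A reader might infer a large inflation of false positives. If 3% or 5% of all non-responders converted, RCC would reach 8.7% or 12.4%. Those are upper illustrations without support in the documents, because only subjects kept on drug by exception or re-treated are at risk. A similar inference about the stage 1 gate in primary refractory melanoma fails too: a 5% conversion rate would exceed that cohort's own 3% null rate, and the cohort was discontinued before full enrollment. Full-N figures for NSCLC PD-L1 high have the same enrollment problem.

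**What to change.** In SAP 7.3.1, state that best overall response and the any-visit responder rule both use assessments up to the earliest of:

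- (a) the date of progression for a confirmed PD, as that section already dates it (the first PD of the confirmed pair);
- (b) the start of new anticancer therapy;
- (c) the first dose of second-course treatment. This is a safeguard, since entry to the second course already requires confirmed PD.

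Say explicitly that responses after an unconfirmed PD still count. List responses seen after confirmed PD or on re-treatment separately, outside ORR and duration of response.

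The cost is one sentence, a date filter in the response program and one listing. Sample sizes, hypotheses and study conduct do not change. The downside is that ORR may fall slightly.

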In an open-label, Phase 1b study, the safety, tolerability, and antitumor activity of pembrolizumab were assessed in subjects with recurrent or metastatic urothelial cancer in the KEYNOTE-012 study (Clinicaltrials.gov: NCT01848834). In this study, archival or newly obtained tumor samples from subjects with advanced carcinoma of the renal pelvis, ureter, bladder, or urethra were screened for PD-L1 expression using a prototype immunohistochemistry assay. PD-L1 expression in stroma or  $\geq 1\%$  of tumor cells was required for study entry. Subjects received pembrolizumab 10 mg/kg Q2W until complete response (CR), progression, or unacceptable toxicity. A total of 33 subjects were enrolled, including 30 with transitional cell histology and 3 with nontransitional cell or mixed histology. Fifty-two percent of subjects received  $\geq 2$  prior therapies for advanced disease, and 21% had liver metastases. Twenty-nine had a baseline scan with measurable disease and were evaluable for response. Objective response rate by RECIST v1.1 central review was 24%. The most common adverse events (AEs) included fatigue (n = 6), peripheral edema (n = 4), and nausea (n = 3); 4 subjects (12%) reported Grade 3-4 drug-related AEs, with only rash seen in > 1 subject (n = 2).

Another cohort from the KEYNOTE-012 study included subjects with SSCHN. In this cohort, pembrolizumab 10 mg/kg was given Q2W. Sixty-one subjects were enrolled (23 human papillomavirus [HPV]+, 37 HPV-). After a median follow-up of 10.2 months, 15 subjects (25%) remained on pembrolizumab. The ORR per RECIST v1.1 by investigator review was 20%, and response duration ranged from 8+ to 41+ weeks (median not reached). The ORR was similar in HPV+ and HPV- subjects, whereas PFS and OS were longer in HPV+ subjects. PD-L1 expression was positively correlated with ORR (p = 0.018) and PFS (p = 0.024). The ORR was 50% in the 12 subjects with high PD-L1 expression. Drug-related AEs of any grade occurred in 58% of subjects (Grade  $\geq 3$  in 17%). The most common drug-related AEs were fatigue (18%), pruritus (10%), and nausea (8%). There were no drug-related deaths.

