### 7.6.2. Tumor Imaging During the Study

Tumor imaging may be performed by CT or MRI, but the same imaging technique should be used in a subject throughout the study. Scans must be a contrast CT or MRI, except in circumstances where there is a contrast allergy or with medical monitor approval. When the CT component of a PET/CT uses higher energy and thinner slices, it may be acceptable (with medical monitor approval) if it was the same technique used for baseline. Imaging should be performed every 9 weeks (63 days  $\pm$  5 days) for the first 2 timepoints (Weeks 9 and 18), then every 12 weeks thereafter. More frequent imaging should be performed if clinically indicated. Imaging should not be delayed for delays in cycle starts or extension of combination treatment cycle intervals.

Per RECIST v1.1, response should be confirmed by a repeat radiographic assessment not less than 4 weeks from the date the response was first documented. The scan for confirmation of response may be performed at the earliest 4 weeks after the first indication of response, or at the next scheduled scan (9 or 12 weeks later), whichever is clinically indicated. Confirmation scans are considered interval scan and subjects need to stay on 9 or 12-week schedule from baseline (eg, imaging at Week 9 shows PR, confirmation scan done at Week 13, next scheduled scan should be Week 18 followed by Week 30, etc).

Imaging should continue to be performed until documented disease progression, the start of new anticancer treatment, withdrawal of consent, death, or the end of the study, whichever occurs first. Disease progression should be confirmed at least 4 weeks after the first scan indicating progressive disease in clinically stable subjects. Subjects who have unconfirmed disease progression may continue on treatment until progression is confirmed provided they have met the conditions detailed in Section 7.6.3.

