### **7.6.3. Assessment of Disease**

#### **7.6.3.1. Assessment of Disease According to Modified RECIST v1.1 for Solid Tumors**

RECIST v1.1 will be applied by the site as the primary measure for assessment of tumor response and as a basis for Protocol guidelines related to disease status (eg, discontinuation of study therapy). RECIST v1.1 will be adapted for defining PD as follows to account for the unique tumor response seen in this class of therapeutics.

If imaging shows PD, tumor assessment should be repeated  $\geq 4$  weeks later to confirm PD with the option of continuing treatment for clinically stable subjects (see Table 16). Clinically stable is defined by the following criteria:

- Absence of signs and symptoms indicating disease progression
- No decline in ECOG performance status
- Absence of rapid progression of disease
- Absence of progressive tumor at critical anatomical sites (eg, cord compression) requiring urgent alternative medical intervention.

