**Table 21: Sample Size Calculation for Each Cohort: Comparing to a Known Proportion**

Tumor Type	ORR		Sample Size
	H0	Ha	
NSCLC high positive (PD-L1 TPS $\geq$ 50%)	36%	56%	42
NSCLC low/negative or indeterminate (PD-L1 TPS 0%-49% or indeterminate)	12%	32%	25
Melanoma (immune checkpoint-naïve)	32%	52%	40
Transitional cell carcinoma of the GU tract	24%	44%	36
TNBC	19%	39%	32
Ovarian cancer	20%	40%	33
SCCHN	19%	39%	32
DLBCL	36%	57%	37
RCC	25%	45%	36
MSI high CRC	57%	80%	29
Gastric cancer	14%	34%	27
HCC	19%	39%	32
Melanoma (primary refractory)	3%	20%	27 a
Melanoma (relapsed)	10%	35%	18 a
Total			446

a Maximum possible sample size for Simon 2-stage design. Actual sample size may be less.

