7.4.2. Duration of Response

For objective responders, the DoR is the time from the first overall response contributing to an objective response (CR or PR) to the earlier of the subject's death or first overall response of PD (by irRECIST v1.1 for selected solid tumors and the modified Lugano Classification for DLBCL) occurring after the first overall response contributing to the objective response. Median DoR and CIs will be estimated using the Kaplan-Meier method. Subjects who are still responding at the time of database freeze or discontinuation will be right-censored at the last valid response assessment date before starting any new anticancer therapy. The DoR evaluation will be performed separately for each treatment group and no statistical comparison will be made.

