2.2 Protocol Deviation			
2.2.1	Protocol Deviations		
2.3 Data Ex	2.3 Data Excluded from Efficacy, and/or Safety Analyses		
2.3.1	Analysis Populations		
2.4 Demogr	raphy and Baseline		
2.4.1	Demographic and Baseline Disease Characteristics		
2.4.2.1	Oncology Disease History (Hepatocellular Carcinoma)		
2.4.2.2	Oncology Disease History (Breast Cancer)		
2.4.2.3	Oncology Disease History (Melanoma)		
2.4.2.4	Oncology Disease History (NSCLC)		
2.4.2.5	Oncology Disease History (Renal Cell Carcinoma)		
2.4.2.6	Oncology Disease History (Squamous Cell Carcinoma of the Head and Neck)		
2.4.2.7	Oncology Disease History (Transitional Carcinoma of the GU Tract)		
2.4.2.8	Oncology Disease History (Ovarian)		
2.4.2.9	Oncology Disease History (Gastric Cancer)		
2.4.2.10	Oncology Disease History (Colorectal)		
2.4.2.11	Oncology Disease History (DLBCL)		
2.4.2.12	Oncology Disease History (Adenocarcinoma of the Endometrium)		
2.4.3	Prior Radiation Treatment		
2.4.4	Prior Medications for Cancer		
2.4.5	Prior Surgery		
2.4.6	Medical History		
2.4.7	Prior and Concomitant Medication		
2.5 Study I	Drug Administration		
2.5.1	Study Drug Administration – INCB024360		
2.5.2	Study Drug Administration – MK-3475		
2.5.3	Study Drug Administration for Subjects Who Entered Monotherapy Period – INCB024360		
2.5.4	Study Drug Administration for Subjects Who Entered Retreatment Period – INCB024360		
2.5.5	Study Drug Administration for Subjects Who Entered Retreatment Period – MK-3475		
2.6 Efficacy	2.6 Efficacy		
2.6.1.1	Investigator-Reported Assessment by irRECIST Criteria (Phase 2 only, not including DLBCL)		
2.6.1.2	Investigator-Reported Assessment by Modified Lugano Criteria (Phase 2 only, DLBCL only)		
2.6.2.1	Duration of Response by irRECIST/Modified Lugano Criteria (Phase 2 only, all tumor types)		
2.6.2.2	Duration of Disease Control by irRECIST/Modified Lugano Criteria (Phase 2 only, all tumor types)		
2.6.2.3	Progression-Free Survival by irRECIST/Modified Lugano Criteria (Phase 2 only, all tumor types)		
2.6.2.4	Overall Survival (Phase 2 only, all tumor types)		
2.6.2.5	Target Lesions (Phase 2 only, not including DLBCL)		
2.6.3.1	Investigator-Reported Assessment by RECIST Criteria (Phase 2 only, not including DLBCL)		
2.6.3.2	Investigator-Reported Assessment by Lugano Criteria (Phase 2 only, DLBCL only)		

Listing No.	Title	

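### Solid-tumor ORR in SAP 7.3.1 counts a single unconfirmed CR or PR, this is not reconciled with the confirmation step in Protocol 7.6.2, and the basis of each H0 is not stated

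*SAP*

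**What the plan says.** Four places bear on who counts as a responder in the solid-tumor cohorts.

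- **Protocol 7.6.2** (imaging during the study): under RECIST v1.1 the rule is that "response should be confirmed by a repeat radiographic assessment not less than 4 weeks from the date the response was first documented". This section also places the confirming scan within the imaging calendar.
- **Protocol 7.6.3.1** (modified RECIST): "RECIST v1.1 will be adapted for defining PD as follows". The adaptation that follows concerns progression only and leaves response confirmation as it was.
- **Protocol 9.4.1** (primary analyses): ORR is "the proportion of subjects with best response (CR or PR) by irRECIST v1.1 for select solid tumors". Confirmation is neither required nor waived.
- **SAP 7.3.1**: a participant is "considered an objective responder as assessed by irRECIST if they have an overall response of CR or PR at any postbaseline visit". That section also sets out a long confirmation algorithm for progression and none for response.

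The responder set carries into SAP 7.4.2: "For objective responders, the DoR is the time from the first overall response contributing to an objective response (CR or PR").

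Each cohort is tested by a one-sample binomial test at one-sided 5% (SAP 3.3 and 7.3.1). The comparator is an H0 from Protocol Table 21, titled "Sample Size Calculation for Each Cohort: Comparing to a Known Proportion", which SAP Table 4 repeats. Both documents describe H0 only as a historical response rate. SAP 10.1 describes a reduction of analyses after enrollment closed and does not mention the responder rule; SAP 10.2 does not mention it either.

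**The concern.** ORR is the primary endpoint of single-arm, open-label, investigator-assessed cohorts, each judged against a fixed number. Any-visit ORR can only equal or exceed confirmed ORR in the same subjects. The comparison therefore means something only if the observed rate and H0 count responses in the same way.

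The Protocol's one statement on confirming response for assessment points one way and the SAP's counting rule points the other. No text explains the choice, and the H0 basis that would settle whether it matters is not given. A reader cannot tell whether a cohort that passes its test did so on activity or on a looser definition of response. Median duration of response is exposed as well, because its population includes responses seen on one scan only.

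**Working it through.** **Inputs.** H0, Ha and N come from Protocol Table 21 / SAP Table 4. The test is one-sided at 5% (SAP 3.3). Power is 80% with 10% lost to follow-up (SAP 3.4.2). The share *u* of any-visit responders who are never confirmed is not in the documents; 5%, 10% and 20% are assumed.

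**Reproducing the plan.** n = ((1.645·√(H0(1−H0)) + 0.842·√(Ha(1−Ha)))/(Ha−H0))², rounded up, then divided by 0.90 and rounded up. For transitional cell carcinoma (24% vs 44%): (1.645×0.427 + 0.842×0.496)/0.20 = 5.60; squared, 31.4, so 32; 32/0.90 = 35.6, so 36, as tabulated. All 12 single-stage sample sizes reproduce this way. The sample-size arithmetic is not in question, and N does not depend on the responder rule.

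**Cohorts shown.** The eight single-stage solid-tumor cohorts that Protocol Table 3 does not mark as discontinued before full enrollment, at planned N. The same definition applies to the other solid-tumor cohorts, but planned N does not describe them.

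**Critical value.** r is the smallest count with P(X ≥ r | N, H0) ≤ 0.05.

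**Case 1: H0 is a confirmed rate and any-visit ORR is tested (the SAP rule).** A cohort whose true confirmed rate is H0 has any-visit rate H0/(1−u), so type I error = P(X ≥ r | N, H0/(1−u)). For transitional cell carcinoma, r = 14. At u = 10% the rate is 0.24/0.90 = 26.7%, and type I error goes from 3.4% to 7.4%.

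| Cohort | N | H0 | r | u=0 | u=5% | u=10% | u=20% | u at which error reaches 5% |
|---|---|---|---|---|---|---|---|---|
| NSCLC low/negative | 25 | 12% | 7 | 2.4 | 3.1 | 4.0 | 7.0 | 14.0% |
| Melanoma, checkpoint-naive | 40 | 32% | 19 | 2.9 | 4.9 | 8.1 | 20.9 | 5.2% |
| Transitional cell | 36 | 24% | 14 | 3.4 | 5.0 | 7.4 | 16.3 | 5.0% |
| TNBC; SCCHN (each) | 32 | 19% | 11 | 2.9 | 4.1 | 5.8 | 11.6 | 7.8% |
| Ovarian | 33 | 20% | 12 | 2.2 | 3.1 | 4.6 | 9.9 | 11.1% |
| RCC | 36 | 25% | 14 | 4.6 | 6.8 | 9.9 | 20.7 | 1.0% |
| Gastric | 27 | 14% | 8 | 2.8 | 3.6 | 4.8 | 8.6 | 10.7% |

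Entries under u are type I error in percent. At u = 5% only RCC is clearly above 5%. At 10%, melanoma, transitional cell, TNBC, SCCHN and RCC exceed it (5 of 8). At 20% all eight do.

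**Case 2: H0 and Ha are any-visit rates and confirmed ORR is tested.** Type I error = P(X ≥ r | N, H0(1−u)); power = P(X ≥ r | N, Ha(1−u)). Ranges over the eight cohorts:

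| u | Type I error | Power at Ha |
|---|---|---|
| 0 | 2.2%-4.6% | 72.4%-81.7% |
| 5% | 1.5%-3.1% | 64.0%-73.6% |
| 10% | 0.9%-2.0% | 52.6%-63.9% |
| 20% | 0.2%-0.8% | 27.4%-46.7% |

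**Case 3: matched bases.** Type I error stays at 2.2%-4.6%.

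**Can the H0 basis be inferred?** Protocol 1.1.3 quotes a urothelial rate of 24% (H0 24%) and a TNBC rate of 18.5% (H0 19%). Neither is tied to Table 21 or described as confirmed. Other rates in that section do not match: gastric 22% against H0 14%, HCC 23% against H0 19%. The basis cannot be recovered from the documents.

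**The case against.** The strongest defense is that the Protocol's statistics section, not its imaging section, defines the endpoint. Protocol 9.4.1 asks for best response of CR or PR without confirmation, and SAP 7.3.1 makes that operational in explicit terms. Protocol 7.6.2 says only that response should be confirmed and is largely about scan timing. Confirmed response has other uses in the Protocol, such as stopping MK-3475 after confirmed CR (5.8.1) and re-treatment eligibility (6.2.1), so a confirming scan has a purpose even if it was never meant as the primary-endpoint rule. These are proof-of-concept tests, now headed for an abbreviated report.

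Much of this stands. A reader might infer that the SAP breaches the Protocol's definition of ORR; it does not, because 9.4.1 is silent and the SAP fills that silence. A reader might also infer that the tests are biased toward success; that follows only if an H0 is a confirmed rate, which no passage says.

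What does not fall away is that the SAP fills the silence without the response-confirmation step in 7.6.2, which 7.6.3.1 leaves intact, and does not record the choice. Being explicit about what is counted does not tell the reader whether H0 was counted the same way.

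It is tempting to go further and make confirmed ORR primary wherever the H0 basis is unknown. On these documents that could mean every solid-tumor cohort. It would change the primary rule after enrollment ended in an open-label study, and case 2 shows the power it could cost. Amendment 10 also ended disease follow-up after treatment (Protocol 6.4.2), so a missing confirming scan may reflect truncation rather than a lost response.

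**Conclusion.** The gap is real and worth fixing. The responder rule in SAP 7.3.1 and the confirmation step in Protocol 7.6.2 are unreconciled, and the basis of H0 is unstated. The consequence is conditional. If an H0 is a confirmed rate and 10% of any-visit responders are never confirmed, one-sided type I error is 4.0%-9.9% instead of 2.2%-4.6%, above 5% in 5 of 8 cohorts. If the H0 is an any-visit rate, the SAP test is not inflated.

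These sizes rest on the assumed unconfirmed share and on planned N. The documents support a comparison that cannot be checked, not a demonstrated bias. The finding is confined to solid tumors; DLBCL is assessed under Lugano and is outside it.

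**What to change.** 1. In SAP 7.3.1, keep the any-visit rule as the stated primary analysis and label it unconfirmed ORR.
2. For each solid-tumor cohort add confirmed ORR: CR or PR with a second CR or PR at least 4 weeks later. Derive it from the per-visit data already planned for SAP Appendix E, Listing 2.6.1.1 ("Investigator-Reported Assessment by irRECIST Criteria (Phase 2 only, not including DLBCL"). Give the exact CI, the binomial test and the number of unconfirmed responders, showing separately those with no later scan.
3. In SAP 7.4.2, report duration of response for confirmed responders as well.
4. State from its source, not from study data, whether each H0 is a confirmed or an any-visit rate. Where it is confirmed, base that cohort's conclusion on confirmed ORR. Where the basis cannot be established, claim success only with both results shown.
5. Record this in SAP 10.1 as a change made after enrollment ended. Leave DLBCL as it is.

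The cost is wording in three SAP sections, one derived flag and a few extra table rows. The downsides are a lower reported ORR in the confirmed analysis, a smaller duration-of-response set, and some late responders left unconfirmed because follow-up ended.
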